#### 10.12 Death/ **Radiation Therapy**

The reporting period for radiation therapy for this study is 30 days.

Any death occurring greater than 30 days after the last radiation dose was administered with an attribution of possible, probable, or definite requires expedited reporting within 24 hours.

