The Study Chairs and the study statistician will review the study at least twice a year to identify accrual, adverse event, and any endpoint problems that might be developing. The Mayo Clinic Cancer Center (MCCC) Data Safety and Monitoring Board (DSMB) is responsible for reviewing the accrual and safety for this trial at least twice a year, based on reports provided by the MCCC Statistical Office.

- 16.91 **Adverse Event Stopping Rules:** As no reactions to  $^{18}\text{F}$ -DOPA have been reported within the institution, toxicity testing reported in the literature revealed no deleterious effects (section 0), and there have been no allergic reactions in all

patients accrued to date on multiple studies MC1078, MC1373, and MC1374, no reactions are anticipated. As such, if either of the two scenarios below occur, enrollment will be suspended so that details of each episode can be examined and a trial recommendation will be formulated and presented to the MCCC DSMB:

- At any point during the AE evaluation of the first 9 AE-evaluable patients, one or more patients is unable to complete PET scanning due to allergic reactions to the tracer.

Or, after 10 or more patients are evaluable for AEs, more than 10% of these patients are unable to complete PET scanning due to allergic reactions to the tracer.

There have been no reports in the literature of the occurrence of nephrogenic systemic fibrosis (NSF) in patients with normal renal function. Additionally, we will use the contrast agent gadobenate dimeglumine, which has been shown to have a high safety profile (lower incidence of NSF in patients with renal failure/insufficiency) compared with many other available Gd-based contrast agents. Therefore no reactions are anticipated. As such, if at any time a patient develops NSF enrollment will be suspended so that details of the episode can be examined and a trial recommendation will be formulated and presented to the MCCC DSMB.

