Using the radiation treatment dosing, fractionation and normal tissue constraints outlined in Section 7 have been performed in several studies without significant adverse effects. While radiation-induced brain necrosis is rare, a cumulative normal brain dose of < 100 Gy in 2 Gy equivalents has been suggested as a constraint to minimize the risk of necrosis.[30] Two large studies reported no grade 3 or higher toxicity and no radionecrosis using the same dosing and fractionation as our protocol.[26, 27] In fact, studies using larger fraction sizes (5 Gy/fraction) reported very low rates of radionecrosis when keeping reirradiation doses under 40 Gy.[28, 29] However, tumor progression is expected in the majority of patients and commonly results in severe neurologic symptoms near the end of life. Both acute (available at <http://ctep.cancer.gov>) and late [39] toxicity will be monitored continuously as each patient is accrued and follow-up data are accumulated. If at any time, 1) 3 or more of the first 9 AE-evaluable patients; or, 2) after 10 or more patients are AE-evaluable, more than 30% experience any of the following adverse effects considered to be at least possibly related to radiation treatment up to and including the three-month timepoint; enrollment will be suspended so the details of each episode may be examined and a trial recommendation will be formulated and presented to the MCCC DSMB, adjusting the dose, fraction size or volumes as needed.

- Grade 3 or 4 irreversible CNS toxicity
- Grade 4 non-hematologic, non-CNS toxicity
- Any Grade 5 toxicity

Initial estimated Primary Completion Date: At study activation, this study will have been registered within the www.ClinicTrials.gov (CT.gov) website. The Primary and Secondary endpoints along with other required information for this study will be reported on CT.gov. For purposes of timing of the CT.gov results reporting, the initial estimated completion date of the primary endpoint of this study is 27 months after the study opens to accrual.

16.101 Definition of Primary-Endpoint Completion Date (PCD): The PCD is the date at which the last progression free patient has been followed for 3 months.

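### In section 16.91, deaths possibly related to radiation count only towards a pooled limit shared with non-fatal toxicity and have no suspension trigger of their own

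*Combined protocol and SAP*

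**What the plan says.** Section 16.91 lists three kinds of event for the radiation rule: "Grade 3 or 4 irreversible CNS toxicity", Grade 4 toxicity that is neither hematologic nor CNS, and "Any Grade 5 toxicity". An event counts if it is at least possibly related to radiation and occurs by the three-month timepoint. All three kinds count towards one limit with two parts: "3 or more of the first 9 AE-evaluable patients", or, once at least 10 patients are evaluable, "more than 30% experience any of the following adverse effects considered to be at least possibly related to radiation treatment". Monitoring is continuous. When the limit is met, enrolment is suspended and a recommendation goes to the DSMB.

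The same section offers this reassurance about radiation: "Two large studies reported no grade 3 or higher toxicity and no radionecrosis using the same dosing and fractionation as our protocol". Its tracer rule suspends enrolment if, during the first 9 patients, "one or more patients is unable to complete PET scanning due to allergic reactions to the tracer". A single case of nephrogenic systemic fibrosis (NSF) also suspends enrolment at any time.

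Deaths are reported fast. Section 10.52 requires a 24-hour report of any death within 30 days of the last radiation dose, whatever the attribution. Under section 10.12, a later death "with an attribution of possible, probable, or definite requires expedited reporting within 24 hours". Neither section states that enrolment is suspended.

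**The concern.** The most serious outcome has the same threshold as the non-fatal ones. The protocol describes its radiation schedule as having caused no Grade 3 or higher toxicity in two large studies, so one related death would already be a departure from expectation. For the tracer and NSF, where it likewise expects no reactions, the section lets a single case pause enrolment. For radiation, two related deaths in the first 9 patients need not do so.

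At stake is whether more patients are enrolled before anyone is obliged to stop and review a related death. DSMB review is required at least twice a year. At the planned 10 patients per year (section 16.4), about 10/2 = 5 patients could enrol between reviews. The clauses on undue toxicity (16.24, 16.3) and on termination (16.6) carry no number.

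**Working it through.** **Plan's own figures.** The documents give limits for the suspension rule but no operating characteristics. The only error rates stated for 20 patients belong to the efficacy design: alpha 0.186 and power 85.9%. An exact two-stage binomial calculation (stop at 1 or fewer of 10, succeed at 6 or more of 20) gives 0.1863 and 0.8586, so those figures reproduce.

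**Inputs.** From 16.91: 3 or more of the first 9; strictly more than 30% from 10 patients on; continuous looks. From 16.3: 20 evaluable patients, 22 at most.

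**Events needed to suspend.** b(n) = 3 for n ≤ 9, and b(n) = floor(0.30 n) + 1 for n ≥ 10.

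| AE-evaluable patients | Events that suspend | Most that do not |
|---|---|---|
| up to 9 | 3 | 2 |
| 10–13 | 4 | 3 |
| 14–16 | 5 | 4 |
| 17–19 | 6 | 5 |
| 20–22 | 7 | 6 |

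At 20 patients, 6/20 = 30.0%, which is not more than 30%. But the limit is checked at every patient, so six events pass only with at most 2 by patient 9, 3 by patient 13, 4 by patient 16 and 5 by patient 19.

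**Orderings that never suspend.** Let c(n,k) be the number of ways to reach k events in n patients without suspension. Then c(n,k) = c(n−1,k) + c(n−1,k−1) if k < b(n), and 0 otherwise. At n = 20:

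| Events | Orderings that pass | All orderings | Share |
|---|---|---|---|
| 2 | 190 | 190 | 100% |
| 3 | 1,056 | 1,140 | 92.6% |
| 4 | 3,542 | 4,845 | 73.1% |
| 5 | 6,764 | 15,504 | 43.6% |
| 6 | 4,107 | 38,760 | 10.6% |
| 7 | 0 | 77,520 | 0% |

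**Chance that the rule fires.** With independent patients and a true rate p of counted events, P(suspend within 20) = 1 − Σ c(20,k) p^k (1−p)^(20−k). For p = 0.10 the terms for k = 0 to 6 are 0.1216 + 0.2702 + 0.2852 + 0.1761 + 0.0656 + 0.0139 + 0.0009 = 0.9335, so the chance is 0.0665. The documents give no value of p; the range below is assumed.

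| Assumed rate p | Rule fires within 20 | At least one event, 1 − (1−p)^20 |
|---|---|---|
| 2% | 0.0006 | 0.33 |
| 5% | 0.0095 | 0.64 |
| 10% | 0.0665 | 0.88 |
| 15% | 0.1873 | 0.96 |
| 20% | 0.3564 | 0.99 |
| 30% | 0.7045 | >0.99 |

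Over 22 patients the rule fires with probability 0.0095, 0.0668 and 0.1897 at 5%, 10% and 15%. These three rows describe a related-death rate only if deaths are the sole qualifying events. If non-fatal events affected as many further patients as deaths did (assumed), a 10% death rate would give a 20% pooled rate and 0.36, and a 15% death rate a 30% pooled rate and 0.70.

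**Chance of a pause with a one-death trigger.** At related-death rates of 1%, 2% and 5%: 1 − 0.99^20 = 0.18, 1 − 0.98^20 = 0.33, 1 − 0.95^20 = 0.64.

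**The case against.** A tolerant limit has a rationale. Section 16.91 itself says that most patients are expected to progress, often with severe neurologic symptoms near death, so attributing a death is hard. Section 1.6 gives median survival after reirradiation of 7 to 10 months. With exponential survival (assumed), 1 − 0.5^(3/10) = 19% to 1 − 0.5^(3/7) = 26% die within three months, about 4 to 5 of 20. If 10% of those deaths were called possibly related, a one-death trigger would fire in 32–41% of trials; at 25%, in 62–74%. The tracer is the investigational agent, while sections 10.41 and 10.11 describe radiation as standard treatment, so the two rules need not match. Expedited reporting, the DSMB and the discretionary clauses also exist. All of this stands as a reason to state the cost of a trigger openly. None of it supplies a defined point at which a related death pauses enrolment.

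Four stronger readings are tempting, and the documents do not support them:

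- A reader might infer that any six deaths in 20 would pass. Continuous monitoring stops 89.4% of the orderings.
- A reader might infer that related deaths feed no trigger. They do count, within the pool, if they occur by three months.
- A reader might take 0.01 to 0.19 as the rule's general performance. Those figures exclude all non-fatal qualifying events.
- A reader might infer that coding keeps progression deaths out. The list of reportable deaths under section 10.12 codes them as Grade 5; only the attribution test in 16.91 excludes them.

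**Conclusion.** The point holds as a gap in the safety rule. Related deaths have no trigger of their own. With no other qualifying event, two in the first 9 patients do not suspend enrolment in any ordering, and up to 6 of 20 can pass if they come late. Any non-fatal qualifying event lowers those counts, and deaths after three months are not counted at all.

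The firing probabilities rest on independent patients, a look after each one, and assumed event rates. The counts rest only on the text. The plan does not contradict itself or miscalculate here, and the primary analysis is unaffected. The right label is a cheap improvement, with the final choice for the sponsor and DSMB.

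**What to change.** Leave the pooled rule in 16.91 unchanged, with Grade 5 events still counted in it; taking them out would weaken it, because a death would no longer add to non-fatal events. Add one sentence: any Grade 5 toxicity judged at least possibly related to radiation, up to the three-month timepoint, suspends enrolment for case review and a recommendation to the DSMB. State alongside it that deaths judged due to progressive disease and unrelated to radiation are excluded by the attribution judgment, not by their coding.

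The cost is one or two sentences and no new data, since these deaths are already reported within 24 hours. The downside is a pause in enrolment for each review, with the probabilities given above, and more pauses if progression deaths are loosely called possibly related.

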#### 16.11 Inclusion of Women and Minorities

This study will be available to all eligible patients regardless of race, gender, or ethnic group.

16.111 There is no information currently available regarding differential effects of this regimen in subsets defined by gender, race or ethnicity, and there is no reason to expect such differences to exist. Therefore, although the planned analyses will, as always, look for differences based on gender and racial groupings, the sample size is not increased in order to provide additional power for such subset analyses. Based on prior studies involving similar disease, we expect about 7% of patients will be classified as minorities by race and about 40% of patients to be women. Expected sizes of racial by gender subsets are shown in the following table:

Ethnic Category	Sex/Gender		
	Females	Males	Total
Hispanic or Latino	1	1	2
Not Hispanic or Latino	8	12	20
Ethnic Category: Total of all subjects	9	13	22
Racial Category			
American Indian or Alaskan Native	0	0	0
Asian	0	0	0
Black or African American	1	1	2
Native Hawaiian or other Pacific Islander	0	0	0
White	8	12	20
Racial Category: Total of all subjects	9	13	22

***Ethnic Categories:***

**Hispanic or Latino** – a person of Cuban, Mexican, Puerto Rican, South or Central American, or other Spanish culture or origin, regardless of race. The term “Spanish origin” can also be used in addition to “Hispanic or Latino.”

**Not Hispanic or Latino**

***Racial Categories:***

**American Indian or Alaskan Native** – a person having origins in any of the original peoples of North, Central, or South America, and who maintains tribal affiliations or community attachment.

**Asian** – a person having origins in any of the original peoples of the Far East, Southeast Asia, or the Indian subcontinent including, for example, Cambodia, China, India, Japan, Korea, Malaysia, Pakistan, the Philippine Islands, Thailand, and Vietnam. (Note: Individuals from the Philippine Islands have been recorded as Pacific Islanders in previous data collection strategies.)

**Black or African American** – a person having origins in any of the black racial groups of Africa. Terms such as “Haitian” or “Negro” can be used in addition to “Black or African American.”

**Native Hawaiian or other Pacific Islander** – a person having origins in any of the original peoples of Hawaii, Guam, Samoa, or other Pacific Islands.

**White** – a person having origins in any of the original peoples of Europe, the Middle East, or North Africa.

**17.0 Pathology Considerations/Tissue Bio specimens:  
None**

## 18.0 Records and Data Collection Procedures

### 18.1 Submission Timetable

#### Initial Material(s)

CRF	Active-Monitoring Phase (Baseline) (Compliance with Test Schedule Section 4.0)
Demographics	≤2 weeks after registration
Institutional Contacts	
Eligibility Checklist	
On-Study Form	
Initial Tumor Form	
Baseline Adverse Event Form FDOPA Pre-injection	
MD Anderson Symptom Inventory-Brain Tumor (MDASI) Questionnaire (Baseline)	
Brief Fatigue Inventory Questionnaire (Baseline)	
Concomitant Medications	
Off Treatment 	
Consent Withdrawal (if applicable)	

1. Submit if withdrawal/refusal prior to RT occurs

#### Test Schedule Material(s)

CRF	Active-Monitoring Phase (Compliance with Test Schedule Section 4.0)			
	≤ 1 week after  F-DOPA-PET scan	≤ 4 weeks after each evaluation during RT	≤ 6 months after end of RT 	≤ 6 months after every clinically indicated MR scan 
Radiation Therapy Reporting Form			X 	
Adverse Event Form	X	X 	X	X
Post  FDOPA Injection	X 			
Patient Status: Clinical Follow-Up/Observation		X	X	X 
MD Anderson Symptom Inventory-Brain Tumor (MDASI) Questionnaire	X	X	X	X

CRF	Active-Monitoring Phase (Compliance with Test Schedule Section 4.0)			
	≤ 1 week after  F- DOPA-PET scan	≤ 4 weeks after each evaluation during RT	≤ 6 months after end of RT 	≤ 6 months after every clinically indicated MR scan 
Brief Fatigue Inventory Questionnaire	X	X	X	X
Adverse Events : Late Toxicities			X	X
Concomitant Medications	X	X	X	X
Notification/ Hospitalizations	At each occurrence			
Off Treatment	Submit ≤2 weeks after registration if withdrawal/refusal occurs after receiving therapy			
Consent Withdrawal				

1. Acute toxicity will be assessed during standard of care monitoring by the radiotherapy team during the course of treatment.
2. Late toxicity will be assessed during standard of care appointments. To be submitted ≤2 weeks after each clinically indicated MR scan.
3. This form should be completed **after** the radiation is completed.
4. Timeframes for submission purposefully large as they do not affect patient care i.e. the data being collected is for investigational use only and no patient decisions will be made with it, which allows us to batch the data for analysis by the study team (e.g. for Radiation Oncologist and Radiologists to contour volumes on image data).
5. See Section 4 for time of assessments.
6. Done approximately 15-20 minutes post injection of F-DOPA after scan is completed and if AE observed a second AE assessment is required <24 hours post injection which is performed by study staff.

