### 16.2 Statistical Design

#### 16.21 Decision Rules

The primary endpoint of this trial is the proportion of patients treated with F-DOPA-PET guided radiotherapy who are alive and have not progressed within 3 months. A success will be a patient who is alive and without evidence of progressive disease within 3 months from registration. Median PFS after bevacizumab failure ranges between 1-2 months.[17, 34] Thus, the largest success proportion where the proposed treatment would be considered ineffective in this population is 20%. The following Simon's Optimum design uses 20 patients to test the null hypothesis that the proportion of successes is at most 20% with an overall significance level (alpha) of 0.186, and a power of 85.9% to detect a true success proportion of 40%.

16.22 After 10 evaluable patients are accrued to this study and followed for at least 3 months, if 2 or more successes are alive and progression-free at 3 months, the results will wait until conclusion of the study. If 1 or fewer patients are alive without evidence of progression at 3 months, the study will be stopped and the treatment will be deemed ineffective in this population.

16.23 After 20 evaluable patients are accrued to this study and followed for at least 3 months, if 6 or more successes are observed we may recommend further testing of this regimen in subsequent studies in this patient population.

16.24 We will not suspend accrual between stages to allow the first 20 patients to become evaluable, unless undue toxicity is observed.

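### Section 18.1 allows post-RT toxicity and status forms up to 6 months, although Sections 16.91 and 16.22 act on those data: the stopping rules are delayed, not disabled

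*Combined protocol and SAP*

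**What the plan says.** The Test Schedule Material(s) table in Section 18.1 sets form deadlines by column. During treatment, Adverse Event and Patient Status forms are due "≤ 4 weeks after each evaluation during RT". After treatment there are two columns, "≤ 6 months after end of RT" and "≤ 6 months after every clinically indicated MR scan"; both include the Adverse Event, Late Toxicities and Patient Status forms. During active monitoring the Late Toxicities form appears in these two columns only. The 1-month and 3-month post-RT visits of Section 4 have no column of their own.

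Footnote 4 says "Timeframes for submission purposefully large as they do not affect patient care", on the ground that "no patient decisions will be made with it"; its example is contouring on image data. Footnote 2 opens with late toxicity and then says "To be submitted ≤2 weeks after each clinically indicated MR scan". Its marker is on the Patient Status cell of the MR-scan column and nowhere else.

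Two rules use data of this kind:
- Section 16.91: "toxicity will be monitored continuously as each patient is accrued and follow-up data are accumulated". Enrolment is suspended if 3 or more of the first 9 patients, or more than 30% once 10 or more are evaluable, have a listed event at least possibly related to radiation, up to the 3-month timepoint.
- Section 16.22: "After 10 evaluable patients are accrued to this study and followed for at least 3 months", the study stops if 1 or fewer are alive and progression-free. Section 16.24 keeps accrual open between stages.

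**The concern.** The reason given for the long windows does not fit these forms. Suspending enrolment and stopping the study are decisions about patients, and they rest on toxicity and 3-month status. A rule described as continuous is only as prompt as the slowest data it is allowed to wait for. Because accrual does not pause, each month of permitted delay means more patients treated after a boundary may already have been crossed. The table also contradicts itself: a 2-week footnote sits in a 6-month column, and its text and its marker point to different forms.

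**Working it through.** **Inputs.** Accrual of 10 per year (16.4); maximum of 22 patients (16.3); look at 10 patients with 3 months of follow-up, final rule 6 or more of 20, p0 20%, p1 40%, alpha 0.186, power 85.9% (16.21 to 16.23); deadlines from 18.1. Assumptions: uniform accrual, so patient k registers at month 12k/10; every registered patient is evaluable; about 1 month from registration to end of RT.

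**1. The plan's own figures.** With X1 and X2 each binomial on 10 patients, P(success) = sum over x = 2 to 10 of P(X1 = x) × P(X2 ≥ 6 − x). This gives 0.1863 at 20% (plan: 0.186) and 0.8586 at 40% (plan: 85.9%). The probability of stopping at the look is 0.8^10 + 10 × 0.2 × 0.8^9 = 0.376 at 20%, and 0.046 at 40%. Form timing does not enter these formulas if the decisions use only the first 10 and first 20 patients.

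**2. Cost of a lag.** Extra patients enrolled = (10/12) × lag in months: 0.4 for 2 weeks, 2.5 for 3 months, 5.0 for 6 months.

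**3. Futility look.** Patient 10 registers at month 12. Enrolled at the look = (10/12) × look month.

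| Deadline applied | Look month | Enrolled | Left of 22 |
|---|---|---|---|
| None | 12 + 3 = 15.0 | 12.5 | 9.5 |
| 2 weeks (footnote 2) | 12 + 3 + 0.5 = 15.5 | 12.9 | 9.1 |
| End-of-RT column | 12 + 1 + 6 = 19.0 | 15.8 | 6.2 |
| Full 6 months after the status date | 12 + 3 + 6 = 21.0 | 17.5 | 4.5 |

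These rows count 3 months from registration, as 16.21 does. If the deciding scan is instead the 3-month post-RT scan (registration + 4 to 4.5 months), the 2-week row becomes 13.8 to 14.2 and the last row 18.3 to 18.8 (look at month 22.0 to 22.5). Patient 20 enrols at month 24.0 and patient 22 at month 26.4, so the look precedes the end of accrual in every row.

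**4. Toxicity rule, unfavourable case.** Suppose patients 1 to 3 all have an event first seen at the 3-month post-RT visit (registration + 4 months) and it is known only from the forms. Patient 3 registers at month 3.6.
- No lag: month 7.6, 6.3 enrolled.
- End-of-RT column (6 months after RT, so 3 months after that visit): month 10.6, 8.8 enrolled.
- 6 months after the visit: month 13.6, 11.3 enrolled. Patient 9 registers at month 10.8, so here the first-9 branch could act only after all 9 had entered.

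**5. Which stopping events depend on the forms.**
- Grade 5: 24-hour report for any death within 30 days of the last radiation dose, and later if possibly related (10.52, 10.12).
- Serious Grade 4: Section 10.81 points to 10.4, with a 24-hour initial report. Hospitalizations deemed disease-related are not reported (10.11).
- Grade 3 irreversible CNS toxicity: if recorded as CNS necrosis, it is exempt from expedited reporting (10.11), so the form deadline governs.

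Section 10.91 also sends serious radiation events through the regular data capture system, and the DSMB works from Statistical Office reports at least twice a year (16.9). Neither supplies a shorter clock for the exempt events.

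**The case against.** The best case for the plan has five parts.

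- *The look is event-driven and does not use toxicity forms.* It has no calendar date and needs survival and progression status. This stands.
- *Patient Status already carries the 2-week footnote.* It does in the MR-scan column, where the figure is then 12.9. If the 3-month visit belongs to the end-of-RT column, there is no marker and the figure is 15.8. Reaching 17.5 requires ignoring the marker, so 17.5 is a ceiling on the registration clock. This stands as a limit on size; that the table supports both readings is itself the defect.
- *Safety data have faster routes.* During-RT forms are due in 4 weeks, hospitalizations are notified at each occurrence, the team keeps an event worksheet and log, and expedited reporting applies. This stands for most stopping events, but not for those exempt from expedited reporting.
- *Six months is a maximum at a single centre whose own oncologists assess the events.* True, and actual delay may be short. The stated deadline still permits the long one.
- *Footnote 4 is marked on no visible cell and its example is contouring.* Its marker may have been lost when the PDF was read, so applying it to the safety forms is an inference. The 6-month column headings cover those forms whether or not footnote 4 does.

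**Conclusion.** The point holds as an inconsistency with a modest, one-directional cost. Section 18.1 permits submission windows that do not match continuous toxicity monitoring in 16.91, the 3-month look in 16.22, or its own footnote 2. The cost is exposure: up to 5 more patients enrolled per 6 months of lag, and 12.9, 15.8 or at most 17.5 enrolled at the look (3 months counted from registration), according to which deadline is read. The weakest spot is Grade 3 irreversible CNS toxicity recorded as necrosis, which is a stopping event without an expedited route. The sizes rest on uniform accrual of 10 per year and, for the end-of-RT reading, about 1 month from registration to end of RT.

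A reader might infer that the two rules cannot work, or that an early stop would spare almost no one. The documents do not support that. Most severe events have a 24-hour route. Even at the full lag from the registration-based endpoint, the look falls at month 21 with about 4.5 of 22 patients still to enrol. Alpha and power are also untouched.

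**What to change.** In Section 18.1:
- Set submission of the Adverse Event, Late Toxicities and Patient Status forms after RT, through the 3-month visit and at each MR visit, to at most 2 weeks, the interval in footnote 2.
- Attach footnote 2 to all of those cells, and align the column headings.
- State that footnote 4 does not cover these forms. Keep the 6-month batch window for contouring, volumetric and QOL data only.

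The cost is table wording and somewhat quicker data entry for about 22 patients at one centre. No new data are collected, and the decision boundaries stay as they are.
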